5.3 Treatment interruption and treatment discontinuation

All dose interruptions or discontinuations must be based on the worst preceding toxicity as graded by the NCI Clinical Toxicity Criteria (NCI-CTCAE version 4.03).

Grade 4 adverse events will lead to permanent discontinuation, irrespective of recovery time, unless otherwise specified. Patients requiring > 2 dose reductions for BYL719 should be permanently discontinued.

Patients should have weekly follow-up for 30 days if they develop an AE after discontinuation of study treatment or resolution of the AE to ≤ grade 1, whichever occurs first, that includes all study assessments appropriate to monitor the event.

5.4 Procedures in case of Overdose

There are no known antidotes for BYL719. Additionally, the dose which constitutes an overdose has not been defined. Doses of study treatment in excess of that specified (350 mg daily) in the clinical study protocol are considered to be an overdose. Patients experiencing toxicity upon overdosing must be treated at the discretion of the treating physician with adequate supportive care as indicated by the symptoms observed in the patient. Patients will have to be followed until full recovery or confirmed stabilization of the events. There is no clinical experience regarding the effect of hemodialysis on decreasing the plasma levels of BYL719 elimination thus far. There have been four events of accidental overdose reported with BYL719 and these were all cases in combination studies. Adverse events associated with the overdose were those expected with the BYL719 known safety profile and included hyperglycemia, nausea, hyperuricemia, hyponatremia, asthenia and rash. Patients fully recovered after some days and supportive medication to treat the associated adverse events experienced with the overdose. Overdose, with or without associated symptoms, should be handled in the same way as a SAE. Signs or symptoms of an overdose that meet the criteria of SAE should be reported as a SAE in the appropriate manner and be documented as clinical sequelae to an overdose.

5.5 Procedures in Case of Pregnancy

To ensure patient safety, each pregnancy in a patient on study treatment must be reported to Novartis within 24 hours of learning of its occurrence. The pregnancy should be followed up to determine outcome, including spontaneous or voluntary termination, details of the birth, and the presence or absence of any birth defects, congenital abnormalities, or maternal and/or newborn complications.

Pregnancy should be recorded on a Clinical Trial Pregnancy Form and reported by the investigator to the oncology Novartis Drug Safety and Epidemiology (DS&E) department. Pregnancy follow-up should be recorded on the same form and should include an assessment of the possible relationship to the Novartis study treatment of any pregnancy outcome. Any SAE experienced during pregnancy must be reported on the SAE Report Form.

Pregnancy outcomes must be collected for the female partners of any males who took study treatment in this study. Consent to report information regarding these pregnancy outcomes should be obtained from the mother.

5.6 Monitoring and Toxicity Management

Each patient receiving at least one dose of BYL719 will be evaluable for safety. The safety parameters include all laboratory tests and hematological abnormalities, physical findings, and spontaneous reports of adverse events reported to the investigator by patients.

Each patient will be assessed periodically for the development of any toxicity as outlined in Section 6 Study Procedures and Observations. Toxicity will be assessed according to the NCI CTCAE v4.03. Dose adjustments will be made according to the system showing the greatest degree of toxicity.

Table 5. Dose Modifications - Criteria for Interruption and Re-initiation of BYL719

Worst toxicity CTCAE v.4.03 Grade	Dose Modifications for BYL719
Investigations (Fasting Plasma Glucose)	
Hyperglycemia	
Always consider consultation with a diabetologist and recommend/reinforce on lifestyle changes as per ADA, i.e. exercise and dietary advice (e.g. small frequent meals, low carb, high fiber, balancing carbs over the course of the day. Three small meals and 2 small snacks rather than one large meal).	
Maintain dose level and remind patient on lifestyle changes*.
 
 • If FPG < 140 mg/dl, consider adding metformin as per guidance below or in cooperation with diabetologist • If FPG 140-160 mg/dl, start/intensify metformin as per guidance below or in cooperation with diabetologist

Grade 1 (> ULN - 160 mg/dL) [> ULN - 8.9 mmol/L]
 
For patients with baseline values between >ULN – 140 mg/dL (ULN – 7.7 mmol/L) this apply only for values > 140 mg/dL (7.7 mmol/L)
	
Metformin 500 mg once daily with dinner. If no gastrointestinal (GI) intolerance after several days, increase to 500 mg bid, with breakfast and dinner. If tolerated, increase to 500 mg with breakfast, and 1000 mg with dinner. If tolerated, 1000 mg bid with breakfast and dinner. If not tolerated, reduce to prior tolerated dose.
 
Monitor FPG as clinically indicated and at least weekly for 8 weeks, then continue checking at least every two weeks until FPG is within baseline values.

Grade 2 (>160 - 250 mg/dL) [> 8.9 - 13.9 mmol/L]	
Maintain dose level and remind patient on lifestyle changes*, exclude confounding factors like e.g. urinary tract infection, consider

	
consultation with a diabetologist and start oral-antidiabetic treatment, e.g. metformin 500 mg bid with breakfast and dinner. If no GI intolerance, increase to 500 mg with breakfast, 1000 mg with dinner. If tolerated, 1000 mg bid with breakfast and dinner. If not tolerated, reduce to prior tolerated dose. Titrate to the maximum tolerated dose over a period of 3 weeks.
 
If FPG is still rising on maximum tolerated dose of metformin or persistently $>160\text{mg/dL}$ ($>8.9\text{ mmol/L}$), add an insulin-sensitizer, e.g. pioglitazone 30 mg (max. dose). Monitor FPG as clinically indicated and at least weekly until FPG resolves to \leq Grade 1
 
 • If FPG does not resolve to \leq Grade 1 within 21 days after institution of appropriate anti-diabetic treatment, reduce BYL719 by 1 dose level • Continue with anti-diabetic treatment and check FPG at least weekly for 8 weeks, then continue checking at least every 2 weeks, alert treating physician if FPG$>250\text{mg/dL}$
Grade 3 ($> 250 - 500\text{ mg/dL}$) [$> 13.9 - 27.8\text{ mmol/L}$]	
Omit BYL719 and confirm fasting status of the assessment. If non-fasting, re-check within 24 hours.
 
Exclude confounding factors like e.g. urinary tract infection and consider consultation with a diabetologist.
 
Administer intravenous hydration and intervention for electrolyte/ketoacidosis/hyperosmolar disturbances as clinically appropriate. Start metformin and titrate as outlined for Grade 2, add pioglitazone as outlined for Grade 2. Insulin may be used for 1-2 days until hyperglycemia resolves, however this may not be necessary in the majority of BYL719-induced hyperglycemia given the short half-life of BYL719.
 
Monitor FPG as clinically indicated and at least twice weekly until FPG resolves to \leq Grade 1.
 
 • If FPG resolves to \leq Grade 1 within 3-5 days, while off study treatment and on metformin, re-start BYL719 and reduce 1 dose level, continue with anti-diabetic treatment and

	
check FPG at least weekly for 8 weeks, then continue checking at least every 2 weeks, alert treating physician if FPG>250mg/dl
 
 • If FPG does not resolve to Grade1 within 3-5 days while off study treatment and on metformin, consult a diabetologist for management of diabetes is strongly recommended. If FPG does not resolve to ≤ Grade 1 within 21 days after institution of appropriate anti-diabetic treatment in cooperation with diabetologist and exclusion of confounding factors e.g. urinary tract infection, permanently discontinue patient from BYL719 treatment
Grade 4 (> 500 mg/dL) [≥ 27.8 mmol/L]	
Omit BYL719 confirm fasting status of the assessment. If non-fasting, re-check within 24 hours.
 
Exclude confounding factors like e.g. urinary tract infection.
 
Administer intravenous hydration and intervention for electrolyte/ketoacidosis/hyperosmolar disturbances as clinically appropriate.
 
Consider cooperation with diabetologist, initiate or intensify medication with appropriate anti-diabetic treatment (see Grade 3), re-check within 24 hours.
 
 • If grade improves then follow specific grade recommendations • If FPG is confirmed at Grade 4 and confounding factors could be excluded, permanently discontinue patient from BYL719

A diabetologist consultation should always be considered.
 
In case metformin is contraindicated or not tolerated even at low dose, another insulin-sensitizer (e.g., pioglitazone) may represent an alternative.
 
For all grades: instruct patient to follow dietary guidelines according to local and/or institutional standards for management of diabetes mellitus (such as those provided by the American Diabetes Association) during the study, e.g., small frequent meals, low carbohydrate content, high fiber, balancing carbohydrates over the course of the day; three small meals and 2 small snacks rather than one large meal
	

Investigations (Hematologic)
	

Neutropenia (ANC)
	
Grade 1 (ANC < LLN - $1.5 \times 10^9/L$) Grade 2 (ANC < $1.5 - 1.0 \times 10^9/L$)	Maintain dose level
Grade 3 (ANC < $1.0 - 0.5 \times 10^9/L$) Grade 4 (ANC < $0.5 \times 10^9/L$)	
Omit dose until resolved to ≤ Grade 1, then:
 
 • If resolved in ≤ 7 days, then maintain dose level

	
 ● If resolved in > 7 days, then ↓ 1 dose level
Febrile neutropenia	
(ANC < $1.0 \times 10^9/L$, with a single temperature of $\geq 38.3^\circ C$ or a sustained temperature of $\geq 38^\circ C$ for more than one hour)	Omit dose until resolved, then ↓ 1 dose level
Thrombocytopenia	
Grade 1 (PLT < LLN - $75 \times 10^9/L$) Grade 2 (PLT < $75 - 50 \times 10^9/L$)	Maintain dose level
Grade 3 (PLT < $50-25 \times 10^9/L$)	
 Omit dose until resolved to ≤ Grade 1, then: 
 ● If resolved in ≤ 7 days, then maintain dose level ● If resolved in > 7 days, then ↓ 1 dose level
Grade 4 (PLT < $25 \times 10^9/L$)	Omit dose until resolved to ≤ Grade 1, then ↓ 1 dose level
Investigations (Renal)	
Serum creatinine	
< $2 \times ULN$	Maintain dose level
2 – 3 $\times ULN$	
 Omit dose until resolved to ≤ grade 1, then: 
 ● If resolved in ≤ 7 days, then maintain dose level ● If resolved in > 7 days, then ↓ 1 dose level
Grade 3 (> $3.0 - 6.0 \times ULN$)	Permanently discontinue patient from BYL719
Grade 4 (> $6.0 \times ULN$)	Permanently discontinue patient from BYL719
Investigations (Hepatic)	
Bilirubin	
(*for patients with Gilbert Syndrome these dose modifications apply to changes in direct bilirubin only)	
Grade 1 (> $ULN - 1.5 \times ULN$)	Maintain dose level with LFTs* monitored as per protocol
Grade 2 (> $1.5 - 3.0 \times ULN$) with ALT or AST $\leq 3.0 \times ULN$	
 Omit dose until resolved to ≤ Grade 1, then: 
 ● If resolved in ≤ 7 days, then maintain dose level ● If resolved in > 7 days, then ↓ 1 dose level
Grade 3 (> $3.0 - 10.0 \times ULN$) with ALT or AST $\leq 3.0 \times ULN$	
 Omit dose until resolved to ≤ Grade 1, then: 
 ● If resolved in ≤ 7 days, ↓ 1 dose level ● If resolved in > 7 days discontinue patient from BYL719
Grade 4 (> $10.0 \times ULN$)	Permanently discontinue patient from BYL719
AST or ALT and concurrent Bilirubin	
AST or ALT > $3.0 \times ULN$ and total bilirubin > $2.0 \times ULN$	Permanently discontinue BYL719

*LFTs include albumin, ALT, AST, total bilirubin (fractionated if total bilirubin > $2.0 \times ULN$), alkaline phosphatase (fractionated if alkaline phosphatase is grade 2 or higher) and GGT. For patients with

Gilbert Syndrome: total and direct bilirubin must be monitored, intensified monitoring applies to changes in direct bilirubin only; the monitoring includes the following LFTs: albumin, ALT, AST, total bilirubin (fractionated if total bilirubin $> 2.0 \times \text{ULN}$), alkaline phosphatase (fractionated if alkaline phosphatase is grade 2 or higher) and GGT.

Patients with grade 0 or 1 at screening experiencing ALT/AST/bilirubin increase \geq grade 2 the liver function tests must be monitored weekly or more frequently if clinically indicated until resolved to \leq grade 1. In case of any occurrence of ALT/AST/bilirubin increase \geq grade 3 the liver function tests must be monitored weekly or more frequently if clinically indicated until resolved to \leq grade 1; hereafter the monitoring should be continued every other week or more frequently if clinically indicated until the end of treatment with study medication. Patients who discontinued study treatment should be monitored weekly, including LFTs or more frequently if clinically indicated until resolved to \leq grade 1 or stabilization (no CTCAE grade change over 4 weeks).

Investigations (Cardiac)

Cardiac – QTc prolongation

QTcF > 500 ms (\geq Grade 3, 4) or > 60 ms change from baseline on at least two separate ECGs	
First Occurrence:
 
 omit BYL719 Perform an analysis of serum potassium and magnesium, and if below lower limit of normal, correct with supplements to within normal limits. Concomitant medication usage must be reviewed Perform a repeat ECG within one hour of the first QTcF of >500 ms or >60 ms from baseline If QTcF remains > 500 ms or >60 ms from baseline, repeat ECG as clinically indicated, but at least once a day until the QTcF returns to < 480 ms. Seek cardiologist input. Once QTcF prolongation has resolved, BYL719 may be restarted at a one lower dose level. 
Second Occurrence: Permanently discontinue patient from BYL719

---	---

Isolated AST or ALT Elevation

Confounding factors and/or alternative causes for increased transaminases like concomitant medications, infection, hepato-biliary disorders, obstruction, liver metastasis, etc. should be excluded before dose interruption/reduction

Grade 1 ($> \text{ULN} - 3.0 \times \text{ULN}$)	Maintain dose level with LFTs ^b monitored per protocol
Grade 2 ($> 3.0 - 5.0 \times \text{ULN}$) 
 For patients with baseline value $\leq 3.0 \times \text{ULN}$ For patients with baseline value $> 3.0 - 5.0 \times \text{ULN}$ 	
 Maintain dose level. Repeat LFTs^b as soon as possible, preferably within 48-72 hours from awareness of the abnormal results; if abnormal lab values are confirmed upon the repeat test, then monitor LFTs^b weekly, or more frequently if clinically indicated, until resolved to $\leq 3.0 \times \text{ULN}$ Maintain dose level

Grade 3 (> 5.0 - 20.0 x ULN) > 5.0 - 10.0 x ULN 
 For patients with baseline value \leq 3.0 x ULN For patients with baseline value > 3.0 -5.0 x ULN 	
 Omit dose. Repeat LFTs^b as soon as possible, preferably within 48-72 hours from awareness of the abnormal results; monitor LFTs^b weekly, or more frequently if clinically indicated, until resolved to \leq 3.0 x ULN Then If resolved in \leq 14 days, maintain dose level If resolved in > 14 days, \downarrow 1 dose level Maintain dose level. Repeat LFTs^b as soon as possible, preferably within 48-72 hours from awareness of the abnormal results; if abnormal lab values are confirmed upon the repeat test, then monitor LFTs^b, weekly, or more frequently if clinically indicated, until resolved to \leq 5.0 x ULN If resolved in \leq 21 days, maintain dose level If resolved in > 21 days and confounding factors have been excluded, \downarrow 1 dose level
> 10.0 - 20.0 x ULN	Omit dose. Repeat LFTs ^b as soon as possible, preferably within 48-72 hours from awareness of the abnormal results; monitor LFTs ^b weekly, or more frequently if clinically indicated, until resolved to \leq baseline. Then \downarrow 1 dose level.
Grade 4 (> 20.0 x ULN) 
 For patients deriving clinical benefit upon investigator's judgement For all other patients 	
 Omit dose. Repeat LFTs^b as soon as possible, preferably within 48-72 hours from awareness of the abnormal results; monitor LFTs^b weekly, or more frequently if clinically indicated, until resolved to \leq 3 x ULN (or \leq 5 x ULN for patients with baseline value > 3.0 -5.0 x ULN), then resume treatment at \square 1 dose level. Only 1 dose reduction is allowed; if reoccurs at > 5 x ULN, discontinue patient from alpelisib. Discontinue patient from alpelisib Repeat LFTs^b as soon as possible, preferably within 48-72 hours from awareness of the abnormal results; monitor LFTs^b weekly, or more frequently if clinically indicated, until resolved to baseline or stabilization over 4 weeks
Cardiac - Left Ventricular Systolic Dysfunction	
Asymptomatic, resting ejection fraction 40-50% or 10-20% drop from baseline	
 Maintain dose level, and continue BYL719 with caution Repeat LVEF within 4 weeks or as clinically appropriate
Symptomatic, responsive to intervention, ejection fraction 20-39% or > 20% drop from baseline	
 Omit BYL719 until resolved* (as defined below), then \downarrow 1 dose level LVEF measurement to be repeated, if not resolved* within 28 days permanently discontinue patient from BYL719 treatment
Refractory or poorly controlled, ejection fraction < 20%	Permanently discontinue patient from BYL719
*The event is considered resolved when the patient is asymptomatic, has a resting ejection	

fraction ≥ 40% and ≤20% decrease from baseline.	
Other Cardiac Events	
Grade 1 or 2	Maintain dose level
Grade 3	Omit dose until resolved to ≤ Grade 1, then ↓ 1 dose level
Grade 4	Permanently discontinue patient from BYL719
Investigations (Gastrointestinal)	
Diarrhea	
Grade 1	Maintain dose level
Grade 2	Omit dose until resolved to ≤ Grade 1, then restart at same dose
≥ Grade 3	Omit dose until resolved to ≤ Grade 1, then ↓ 1 dose level
Stomatitis/Oral mucositis	
Grade 1/Tolerable Grade 2	Maintain dose level. Non-alcoholic or saltwater mouth wash.
Intolerable Grade 2 or Grade 3	First occurrence: hold until ≤ Grade 1 and ↓ 1 dose level (if stomatitis is readily manageable with optimal management, re- introduction at the same level might be considered at the discretion of the investigator). Second occurrence: hold until ≤ Grade 1 and ↓ 1 dose level.
Grade 4	Permanently discontinue patient from BYL719
Skin and subcutaneous tissue disorders	
Consultation with a dermatologist is highly recommended for better assessment and management of BYL719-induced skin toxicity. Dermatologist consult is mandated for serious cutaneous reactions (i.e., fulfilling seriousness criteria for AE Reporting) and for severe cutaneous reactions like Stevens-Johnson-Syndrome, Toxic Epidermal Necrolysis, Erythema Multiforme.	
Grade 1 (<10% body surface area (BSA) with active skin toxicity*)	
Maintain dose level
 
 Initiate topical corticosteroids 3-4 x daily, preferred compounds to use are Triamcinolone, Betamethasone as long as skin toxicity is active, during maximum 28 days 
For patients with symptoms like burning and/or pruritus add non-sedating anti-histamine, consider adding a sedating anti-histamine at night If active rash is not resolved within 28 days of appropriate treatment, consider adding low dose systemic corticosteroid (20-40 mg/d)

Grade 2 (10-30% BSA with active skin toxicity*)	
Maintain dose level.
 
 Initiate topical corticosteroids 3-4x daily, preferred compounds to use are

	
Triamcinolone or Betamethasone as long as skin toxicity is active, during max. 28 days
 
 Consider adding systemic corticosteroids 20-40mg/d 
If rash resolves to ≤ G1 within 10 days systemic corticosteroid may be discontinued
 
For patients with symptoms like burning, stinging and/or pruritus add non-sedating anti-histamine, consider adding a sedating anti-histamine at night

Grade 3(>30% BSA with active skin toxicity*)	
Omit BYL719 dose until rash /skin toxicity is no longer active but fading (G1), consider exploratory skin biopsy for central assessment
 
 Initiate topical corticosteroids 3-4x daily, preferred compounds to use are Triamcinolone or Betamethasone for at least 28 days Add systemic corticosteroids 20-40mg/d 
If rash resolves to ≤ G1 within 10 days systemic corticosteroid may be discontinued
 
For patients with symptoms like burning, stinging and/or pruritus add non-sedating anti-histamine during day time, consider adding a sedating anti-histamine at night
 
Re-start BYL719 dose once rash /skin toxicity is no longer active but fading (G1):
 
 - at same dose in case of first occurrence, at reduced dose level in case of second occurrence - If rash/skin toxicity still active in up to 10% BSA after more than 14 days, continue oral corticosteroid for at least 48 hours upon re-challenge with BYL719; if rash and/or pruritus do not reoccur within 48 hours after re-challenge with BYL719, systemic corticosteroid may be discontinued 
For patients with symptoms like burning, stinging and/or pruritus antihistamine regimen should be continued for a minimum of 28 days after re-challenge with BYL719.

Grade 4 (any % BSA associated with extensive superinfection, with IV antibiotics indicated; life-threatening consequences)	
 -Permanently discontinue patient from BYL719 and consider a dermatology consult, , ensure documentation by imaging like photographs, and obtain a skin biopsy. 
Treatment of rash may follow guidelines for Grade 3/ above with the exception of rechallenge. Additional measures may be taken as per local treatment guidance.

Any Grade of Stevens-Johnson-Syndrome/Toxic Epidermal Necrolysis or other SJS/TEN-like severe skin reactions	
 Permanently discontinue patient from alpelisib treatment 
 Consult dermatologist, ensure documentation by imaging like photographs and obtain skin biopsy for central assessment 
Follow local treatment guidelines for SJS/TEN

Investigations (Pulmonary disorders)	
Pneumonitis	
 In patients who have new or worsening respiratory symptoms or are suspected to have developed pneumonitis, interrupt PIQRAY immediately and evaluate the patient for pneumonitis. Permanently discontinue PIQRAY in all patients with confirmed pneumonitis.
Investigations (any other)	
Other adverse events	
Grade 1 or 2	Maintain dose level
Grade 3	Omit dose until resolved to \leq grade 1, then \downarrow 1 dose level
Grade 4	Omit dose and then discontinue from study drug treatment Omit dose for \geq grade 3 vomiting or grade 3 nausea only if the vomiting or nausea cannot be controlled with optimal antiemetic (as per local practice)

6 Study Procedures and Assessments

The study-specific assessments are detailed in this section. All on-study visit procedures are allowed a **window of ± 5 days** unless otherwise noted. Treatment or visit delays for public holidays or weather conditions do not constitute a protocol violation.

A written, signed, informed consent form (ICF) and a Health Insurance Portability and Accountability Act (HIPAA) authorization must be obtained before any study-specific assessments are initiated. A copy of the signed ICF will be given to the subject and a copy will be filed in the medical record. The original will be kept on file with the study records.

All patients who are consented will be registered in OnCore[®], the Banner University Medical Center Clinical Trial Management System (CTMS). The system is password protected and meets HIPAA requirements.

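### The liver rows of the dose-modification table leave one bilirubin/transaminase combination with only maintain-dose rows and, on one reading of *or*, put another combination in two rows that conflict on restart

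*Combined protocol and SAP*

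**What the plan says.** Table 5 in Section 5.6 handles liver results in three places.

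- **Bilirubin rows.** Grade 2 (above 1.5 to 3.0 x ULN) and Grade 3 (above 3.0 to 10.0 x ULN) are each qualified by "with ALT or AST" at or below 3.0 x ULN. Both omit the dose until recovery to Grade 1 or better. For Grade 2 the next step is "If resolved in ≤ 7 days, then maintain dose level", or one level down if recovery takes longer. For Grade 3 it is one level down if resolved within 7 days, otherwise discontinuation.
- **Concurrent row.** Under "AST or ALT and concurrent Bilirubin", AST or ALT above 3.0 x ULN together with total bilirubin above 2.0 x ULN means permanent discontinuation.
- **Transaminase block.** Under "Isolated AST or ALT Elevation", Grade 2 (above 3.0 to 5.0 x ULN) maintains the dose whatever the baseline value. The word isolated is not defined.

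A residual row at the end of the table, for other adverse events, maintains the dose at Grade 1 or 2.

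Sections 5.2 and 5.3 base dose changes on the worst preceding toxicity. Section 5.6 adds that the organ system with the greatest toxicity governs.

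**The concern.** A dose-modification table should return one action for any set of results. Here the qualifier on the bilirubin rows and the entry condition of the concurrent row are not complements of each other. The first turns on transaminases at 3.0 x ULN with bilirubin from 1.5 x ULN. The second turns on transaminases at 3.0 x ULN with bilirubin from 2.0 x ULN. That leaves room for a combination that meets neither. Because both conditions are written with *or*, there is also room for one that meets both.

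At stake is consistent handling of a patient with two raised liver signals shortly before potentially curative surgery. In the gap, the rows that remain are milder than the row for a patient with the same bilirubin and lower transaminases. In the overlap, two sites could differ on whether the same patient may ever restart. If the rise is found on an early unscheduled test, that difference could also decide whether the patient reaches the 10 doses needed to be evaluable (Sections 7 and 10.2.1).

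**Working it through.** The plan has no figure to reproduce. The check sets the row conditions side by side and applies them to test patients. All values are multiples of ULN. Baseline transaminases are assumed to be at or below 3.0 (the entry limit in Section 3.3.1 is 2.5).

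The qualifier on the bilirubin rows can be read in two ways:

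- **Reading A:** at least one of ALT and AST is at or below 3.0.
- **Reading B:** both are at or below 3.0.

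The concurrent row requires max(ALT, AST) > 3.0 and bilirubin > 2.0.

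| Bilirubin | ALT | AST | Reading A | Reading B |
|---|---|---|---|---|
| 1.8 | 2 | 2 | Bilirubin Grade 2: omit | Bilirubin Grade 2: omit |
| 1.8 | 4 | 2 | Bilirubin Grade 2: omit | No bilirubin or concurrent row; what is left says maintain |
| 1.8 | 4 | 4 | No bilirubin or concurrent row; what is left says maintain | Same as A |
| 1.8 | 7 | 7 | No bilirubin or concurrent row; transaminase Grade 3 row: omit | Same as A |
| 2.5 | 2 | 4 | Bilirubin Grade 2 (omit, restart allowed) and concurrent (permanent stop) | Concurrent only |
| 2.5 | 4 | 4 | Concurrent only | Concurrent only |
| 5 | 8 | 2.5 | Bilirubin Grade 3 (omit, restart if resolved within 7 days) and concurrent (permanent stop) | Concurrent only |
| 5 | 8 | 8 | Concurrent only | Concurrent only |

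**Extent on a grid.** Take five bilirubin bands (up to 1.5, >1.5–2.0, >2.0–3.0, >3.0–10, >10) and six bands for each transaminase (normal, up to 3, >3–5, >5–10, >10–20, >20). Two transaminase bands lie at or below 3.0 and four above. Cells count combinations of bands, not patients.

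- **Gap, reading A:** bilirubin >1.5–2.0 with both transaminases above 3.0. That is 4 x 4 = 16 cells. In 1 of them (both >3–5) only maintain rows are left.
- **Gap, reading B:** bilirubin >1.5–2.0 with at least one transaminase above 3.0. That is 36 − (2 x 2) = 32 cells. In 5 of them the higher transaminase is >3–5 and only maintain rows are left: (2 x 2) with the other at or below 3.0, plus 1 with both in that band.
- In the remaining gap cells a transaminase exceeds 5.0. The transaminase rows then omit the dose or, at Grade 4, omit or discontinue.
- **Overlap, reading A:** two bilirubin bands (>2.0–3.0 and >3.0–10) with one transaminase above 3.0 and the other not. That is 2 x (2 x 2 x 4) = 32 cells.
- **Overlap, reading B:** 0 cells.

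Neither reading repairs the table. Reading A gives the overlap and the narrower gap. Reading B removes the overlap and widens the gap.

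**Do the general rules choose a row?** The rule on the governing organ system works between systems, and all these rows concern one system. The worst-toxicity rule does not separate the rows at 1.8/4/4 or 2.5/2/4, where both abnormalities are Grade 2 by the table's own labels. The concurrent row carries no grade, so it cannot be ranked in that way.

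**The case against.** **Default, not instruction.** No row expressly says to maintain the dose in the gap. One candidate sits under a heading for isolated transaminase rises, and a patient with Grade 2 bilirubin is not isolated in plain meaning. The other is a residual row, although liver events have their own block. This stands: the gap is silence filled by default. It does not remove the defect, because isolated is undefined and no other row is offered.

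**Opposite actions.** A reader might infer that the table gives one patient opposite instructions, so that dosing can continue through combined rises in general. The documents do not support that. Every overlap row stops drug at once, and the rows differ only on restart. Bilirubin above 2.0 with both transaminases above 3.0 is a permanent stop on either reading. Continued dosing is confined to the gap.

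**Stopping rule.** A reader might also infer that the choice of row generally alters the Table 8 count. Section 10.3.1 counts discontinuations for qualifying toxicity, which for a non-hematologic event means Grade 3 or higher, intolerable despite optimal management, or delaying surgery beyond 42 days. At bilirubin 2.5 with AST 4.0 both values are Grade 2, so a permanent stop would not ordinarily count. The Grade 3 bilirubin overlap is where the count would ordinarily be affected. A Grade 2 bilirubin case could count if the raised transaminase were itself Grade 3.

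**Mitigation.** Section 3.4 lets the investigator stop treatment for any laboratory abnormality. Section 5.6 requires at least weekly liver tests after a rise to Grade 2 or more from Grade 0 or 1 at screening. Full liver tests are scheduled only once on treatment, within 5 days before surgery (Table 6.1, note d), so triggers should be few and restart is often moot by then. All of this limits frequency and consequence. Discretion does not reconcile written rows, and when surgery is delayed, drug continues without a required repeat of that test (Section 6.2.4).

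**Conclusion.** The liver rows need reconciling, on two specific points.

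1. **Gap, on any reading.** With bilirubin >1.5–2.0 x ULN and both ALT and AST >3.0–5.0 x ULN, only maintain rows are left, while the same bilirubin with ALT and AST of 2.0 x ULN leads to omission. If the qualifier means both transaminases, the gap also takes in patients with just one of them >3.0–5.0 x ULN.
2. **Overlap, only if the qualifier means either transaminase.** With bilirubin >2.0–10 x ULN and one transaminase above 3.0 x ULN and the other not, a row that can permit restart and a permanent-stop row both apply.

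This is an inconsistency in a safety rule, not just missing detail, because the written conditions produce it and the general tie-breaks do not resolve it. The affected region is small. The documents give no rate for these combinations, so no expected number among the 20 planned patients can be stated. The conclusion rests on the row conditions as printed and on baseline transaminases at or below 3.0 x ULN.

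**What to change.** Amend Table 5 in Section 5.6 so that the bilirubin, concurrent and isolated AST/ALT rows are reconciled and each combination of bilirubin, ALT and AST meets exactly one row. State whether the qualifier on the bilirubin rows refers to either transaminase or to both, and state what isolated means. The sponsor must decide which action applies in the gap and in the overlap; this review proposes none. Listing the revised rows against the bilirubin and transaminase bands used above would confirm that none is left uncovered or covered twice.

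The cost is table wording in an amendment. No additional tests, visits or patients are needed.
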